Visual tests: Tests of vision will be conducted on both sides of space and are organized in trials. In each trial the subject acquires fixation for 500 ms before a stimulus is presented after a randomized delay (200-600 ms). Subjects are required to saccade or point to (i.e., “indicate”) the stimulus or stimulus-target (<10° error) within 2 seconds or their response is scored as a “No-Go”. They are informed of whether their response was “correct” or “incorrect” via an auditory tone after a confidence report (see below). Each test has one or more stimulus levels that are manipulated to create the independent variable(s) of psychometric functions of performance. Detection/Localization: Trials contain either a visual target (LED or 5X5° white square) of manipulated contrast at a randomly-selected location outside of central space (correct response: indicate), or no stimulus anywhere (correct response: No-Go). Competition: Trials contain either no stimuli (correct response: No-Go), or 1 stimulus at a randomly-selected location on either side of space (correct response: indicate), or 2 identical visual stimuli at homotopic locations with randomized eccentricity (correct response: indicate both). Stimulus contrast is manipulated. Multisensory Integration: Trials contain either no stimuli (correct response: No-Go) or brief (100 ms) low-contrast visual or low-volume auditory stimuli presented alone or together at a randomly-selected location (correct response: “indicate”). This evaluates whether the senses can be used synergistically in contralesional space to enhance localization as in intact subjects. Frequency Discrimination: Pairs of oriented gratings with manipulated Δ° and Δf presented on either side of space (correct response: indicate if same, No-Go if different). Shape Discrimination: Unilaterally-presented pairs of simple Efron shapes (see (Whitwell et al., 2014)) with manipulated similarity (correct response: indicate if same, No-Go if different). These shapes consist of stacked rectangles or smoothed splines whose similarity can be quantitatively manipulated and provide a robust, common, and controlled way of assessing shape perception in normal and compromised populations. Subjects will also have the opportunity to report qualitative aspects of any changes in their visual perception during the study.

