Testing conditions: Each of the above tests will be evaluated under two different ambient light conditions: normal indoor levels (~300 lux) and darkness (~.001 lux). Lighting conditions are set during the “briefing” period and changed during the “break” (see below), which gives time for dark- or light-accommodation. We will also evaluate conditions in which stimuli are either stationary or moving.

Confidence reports: Subject performance is tracked online and summarized in a numeric “game score” displayed to them after each testing run (see below). On each trial, after making their response (either indicating or No-Go), subjects verbally report a confidence score of 1-3 indicating their confidence in whether they are guessing (1), are unsure (2), or are very confident (3) in their response. The confidence rating translates to the points wagered for that trial. Correct responses increase the game score by double the wagered amount, while incorrect responses decrease the score by the wagered amount.

Testing structure: A 2 hr testing session is divided into two 45-min sets separated by a 10 min “break”, with a 10 min “briefing” period at the beginning and 10 min “recapitulation” period at the end.

Training/testing sessions contain only a single set. Each trial requires <3-5 seconds. Trials of a single task, stimulus level, and testing condition are conceptually organized into “runs” of 10-12 trials (~.75-1 min/run with warmup/cooldown). Two runs with the same task and testing condition, but 1-4 stimulus levels, are intermixed within a “block” of 20-96 trials (2-8 min/block). This structure provides ample time to test two blocks of each visual test (e.g., one block stationary, the other moving) within each set. However, testing will be customized for each subject in this pilot to focus on performance limits; e.g., by reducing testing of basic capabilities in later sessions, not extensively testing multiple levels of higher-order capabilities when lower-level ones are not yet intact, and initially testing with wider ranges of stimulus levels before proceeding to narrower ranges.

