Outcome Measure(s). A variety of dependent measures are extracted during these experiments, including responses selected, response delay/timing, response accuracy, etc. Responses to visual stimuli will be evaluated over the duration of the experiment to assess recovery of function. The main hypotheses state that subjects will either be able to perform some task at some level or not at all, although there is likely to be quantitative variation in parameters such as response latency, threshold sensitivity, and confidence. In this context, recovery of any visual function is a success. Below we outline two sets of predictions identifying the most credible outcomes and elaborate on the significance of each, although mixed results are also possible.

Modest Rehabilitation: It is possible that hemianopic patients will recover basic reflexive visual functionality, but their capabilities will be limited to those typically associated with “blindsight”. In this case, they would be able to detect and localize visual stimuli in the rehabilitated field and use auditory information to enhance this capability. However, they would always choose the intact field in competition tasks, be unable to perform any higher-order discriminations in the contralesional field, and would always

have low confidence in that field even when they can perform visually – a result falling short of that seen in the animal model. Such a result will be less than expected but is not without clinical value: by acquiring the ability to respond to contralesional visual stimuli, rehabilitated subjects can bring them into the sighted field for further analysis.

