The Expected Result: However, our expectation is that hemianopic patients will recover visual functionality similar to that observed in the animal model, although the timing of the recovery and the quantitative parameters of the functional endpoints may differ. This means that, after a few weeks of training, they will be able to perform each of the tasks at some level under some conditions. We expect performance to be best under scotopic conditions and for moving stimuli; i.e., testing conditions best suited to driving robust visual responses in SC-mediated visual pathways. There is likely to be an initial separation between performance in visual tasks and confidence, with the former recovering faster than the latter, as the brain adapts and reinterprets activity patterns in remaining circuits as definitive of the visual stimuli generating them.

In either case, future directions will examine the means to improve the rehabilitation method (including calibrating subjects to the sensation of contralesional visual stimuli), examining the impact of the strategy on other domains impacting quality of life (e.g., navigation), an analysis of the underlying circuits using magnetoencephalography, evaluation of the sensitivity of different individual features to the procedure (e.g., age, gender, delay from lesion onset to treatment), a deeper exploration of the limits of functional recovery, and the formalization of a clinical trials protocol.

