Analytical Plan. The Humphrey visual field test, kinetic visual field test, and low-vision visual functioning questionnaire (LV-VFQ-48) are standard clinical tests of vision administered before and after training. We expect increases in the number of detected locations and decreases in the thresholds of detection (when detected) at each test location in the hemianopic field, for at least Goldmann size V stimuli and smaller, and significant improvements in quality of life. In addition to these common clinical assays, a more detailed picture of low- and high-level vision will be obtained from the tests described above, which produce psychometric functions (curves relating % correct responses to stimulus level) for each subject and location or side of space. Parameters of these functions describing thresholds and maximum accuracy will, alongside confidence scores and latency, be evaluated for changes over time and across subjects and sides of space in a multilevel multivariate regression model (Gelman and Hill, 2007). Maximum likelihood estimation will be used to estimate parameter distributions to guide future studies.

Human Subjects Protection

Subject Recruitment Methods. Patients will be recruited from the local subject population hospitalized/seen by Neurology at Atrium Health / Wake Forest School of Medicine. To maximize the potential for success, adults (<85) of either sex will be selected based on: (1) diagnosis of a stable homonymous hemianopia (>4 weeks) with absence of hemineglect, (2) a lesion encompassing at least primary visual cortex but sparing parietal cortex, (3) normal auditory and cognitive function, (4) willingness to participate in the three month program, (5) ability to perform the visual discriminations in their intact field. Subjects not meeting these criteria are either poor candidates for rehabilitation given the extent of the deficit relative to the known circuits responsible for recovery in animals (crit. 1-2), will not be suitable for the visual-auditory training paradigm (crit. 3-4), or have visual capabilities that cannot be adequately tested (crit. 5). Multiple (n=6) subjects will be recruited for left- and right-sided lesions. Because this is a pilot program, variance across other demographics (e.g., age, gender, race, stroke type) will be noted but are unlikely to be able to be statistically evaluated.

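### Confidence is compared between sides and over time without holding accuracy equal, so neither contrast can by itself show that confidence is dissociated from performance.

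*Combined protocol and SAP*

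**What the plan says.** The document is a combined protocol and SAP. Four places bear on the point.

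- **Outcome Measure(s), Modest Rehabilitation.** The blindsight-like result has three features. The first two describe behaviour on the tasks: "always choose the intact field in competition tasks, be unable to perform any higher-order discriminations in the contralesional field". The third is about ratings, which are expected to be low throughout, so that participants "have low confidence in that field even when they can perform visually". No cut-off for low confidence is given, and no accuracy level or reference field. The same section allows mixed results.
- **Outcome Measure(s), The Expected Result.** "There is likely to be an initial separation between performance in visual tasks and confidence", with performance recovering first. The text attributes this to the brain adapting and reinterpreting activity in the remaining circuits.
- **Analytical Plan.** The tests yield psychometric functions ("curves relating % correct responses to stimulus level") for each participant and location or side. For the threshold and maximum-accuracy parameters of these functions, the plan states this analysis: "alongside confidence scores and latency, be evaluated for changes over time and across subjects and sides of space in a multilevel multivariate regression model".
- **Visual tests, Confidence reports and Testing structure.** "Each test has one or more stimulus levels that are manipulated to create the independent variable(s) of psychometric functions of performance". On every trial the participant states whether they are "guessing (1), are unsure (2), or are very confident (3) in their response". The rating is also a wager: a correct response gains twice the rating and an incorrect one loses the rating. Levels are customised for each participant towards performance limits.

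Nothing in these sections sets levels to equalise accuracy between sides, or models confidence given accuracy.

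**The concern.** In ordinary vision, confidence falls as accuracy falls. A recovering field is likely to be less accurate than the intact field, so it would show lower mean confidence even if confidence and performance were linked in exactly the same way on both sides. Putting stimulus level in the model does not remove this, because the same level gives lower accuracy on the weaker side. Requiring that participants can perform asks for some performance, not equal performance.

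The same problem affects the time course. Confidence and accuracy need not rise at the same rate on their own scales, so an observer whose confidence rule never changes can appear to gain confidence late. The predicted separation could then be reported as confirmed without any change in awareness.

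At stake is the interpretation of one of the named measures of this pilot. The Analytical Plan intends its estimates to guide later studies, so a side or time effect on confidence that mostly restates accuracy would be carried forward as something else.

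**Working it through.** The plan gives no figure for confidence or accuracy by side, so there is nothing to reproduce. The check asks whether an observer with no dissociation would produce the contrasts that the plan will examine.

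**From the document:** the 1-3 confidence scale; the wager payoff; runs of 10-12 trials, two runs per block.

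**Assumed:** a two-choice, equal-variance signal-detection observer. Evidence is x ~ N(m, 1), accuracy is Φ(m), and confidence is 1, 2 or 3 as |x| falls below c1, between c1 and c2, or above c2, with the same cut-points on both sides. Mean confidence = 1 + P(|x| > c1) + P(|x| > c2).

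**1. Accuracy alone moves confidence.**

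| Cut-points c1/c2 | Mean at 90% correct | Mean at 65% correct | Difference |
|---|---|---|---|
| 0.5 / 1.5 | 2.24 | 1.80 | 0.44 |
| 0.7 / 1.4 | 2.20 | 1.71 | 0.49 |
| 0.3 / 1.0 | 2.52 | 2.13 | 0.39 |

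A wider gap gives more. With cut-points 0.7/1.5, the mean is 2.40 at 95% correct and 1.68 at 65%, a difference of 0.72. In a detection version (criterion 1.0, cut-points 0.6 and 1.4 above it), mean confidence on hits is 2.50 at 94.5% hits and 1.82 at 60%, a difference of 0.68.

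**2. Same stimulus levels, weaker side** (cut-points 0.5/1.5; intact m = 0.67, 1.28, 1.88, 2.50; weaker sides multiply m by a gain).

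| Side | Accuracy by level | Confidence by level | Mean |
|---|---|---|---|
| Intact | 0.75, 0.90, 0.97, 0.99 | 1.91, 2.24, 2.57, 2.82 | 2.38 |
| Half gain | 0.63, 0.74, 0.83, 0.89 | 1.79, 1.89, 2.04, 2.22 | 1.99 |
| Quarter gain | 0.57, 0.63, 0.68, 0.73 | 1.76, 1.79, 1.83, 1.89 | 1.82 |

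The unmatched side difference is 2.38 − 1.99 = 0.39 or 2.38 − 1.82 = 0.56, with no dissociation built in.

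**3. At equal accuracy.** For these observers the difference is zero by construction (1.91 on either side at 75% correct). If the evidence that feeds confidence is scaled by an assumed 0.4, a true dissociation, the difference persists: 1.31 against 1.91 at 75%, and 1.53 against 2.24 at 90%. The matched contrast separates the two explanations. The unmatched one does not.

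**4. Apparent lag.** Let one observer with fixed cut-points 0.5/1.5 recover from 50% to 97% correct. Mean confidence goes from 1.75 to 2.57.

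- At 80% correct, accuracy has covered (0.80 − 0.50)/(0.97 − 0.50) = 64% of its range. Confidence (1.99) has covered (1.99 − 1.75)/(2.57 − 1.75) = 29%.
- At 90% correct, the figures are 85% and 59%.

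Confidence trails although the rule never changes.

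**5. Wager.** With rating w and probability correct p, the expected score is 2wp − w(1 − p) = w(3p − 1). This is positive whenever p > 1/3, so a strict score-maximiser always reports 3 above that point, and the effect of accuracy on confidence disappears.

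**6. Precision of matching.** One block gives 2 × 10 = 20 to 2 × 12 = 24 trials per level. At 75% correct, the SE of accuracy is √(0.75 × 0.25/20) = 0.097 to √(0.75 × 0.25/24) = 0.088, if all those trials fall on one side.

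**The case against.** A reader might infer that weak but normal vision will be labelled blindsight. The document does not support that. Its pattern joins three features, and a participant who manages any higher-order discrimination falls outside it whatever the confidence scores. Mixed results are allowed, and nowhere is the side contrast in the Analytical Plan made the rule that separates the two predicted outcomes. The sentence about low confidence makes no side comparison either, and it says always low. The half-gain observer rises to 2.22 at the highest level, and the two-choice observer at 65% correct (cut-points 0.7/1.5) still reports 3 on 16% of trials. All of this stands. The protection has a limit: the quarter-gain observer stays nearly flat (1.76 to 1.89), and vision that weak could also fail the competition and discrimination tests.

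It can also be said that accuracy and confidence enter one multivariate model, so the matched contrast is recoverable from planned data. That is true of the data, but separate side effects on two outcomes are not a side effect on confidence at equal accuracy unless that is specified.

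The size is open to challenge, since cut-points and accuracy gaps are assumed and the payoff could shrink the effect to nothing for a strict score-maximiser. That also stands. Finally, this is a six-person proof-of-concept study with qualitative principal hypotheses, in which recovery of any visual function counts as success. That limits the weight of the point. It does not help with the predicted lag, to which the three-feature pattern offers no protection.

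**Conclusion.** The concern holds as a gap in the specified analysis. As written, neither the side contrast in confidence nor a lag of confidence behind performance can distinguish weaker vision under an unchanged confidence rule from a true dissociation. Weak normal vision could add to a blindsight-like reading but could not produce it through confidence alone.

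The direction follows from any fixed rule of the kind modelled. The size, about 0.4 to 0.7 points on a scale with a 2-point range, is illustrative: it rests on the assumed signal-detection model, cut-points and accuracy gaps, and may be smaller if participants respond to the payoff. No principal conclusion of the pilot depends on it. It is a worthwhile and inexpensive improvement, not a fatal flaw.

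**What to change.** In the Analytical Plan:

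- Specify that side and time effects on confidence are estimated at equal fitted accuracy. Model trial-level confidence on each participant's fitted accuracy by side, pooled over blocks. Alternatively, compare type-2 sensitivity by side, meaning how well confidence separates correct from incorrect responses.
- Handle no-stimulus trials separately, since they belong to neither side.
- State what counts as low confidence.
- Interpret low blind-field confidence, or a confidence lag, as a dissociation only if it remains at equal accuracy.

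In Testing structure, keep some intact-field stimulus levels hard enough for accuracy there to overlap with the blind field.

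**Cost:** somewhat more modelling and some intact-field trials spent at hard levels, with no extra visits. Both sides are already tested at manipulated levels with confidence on every trial. Matching from a single block would be imprecise (SE about 0.09 at 75% correct), which is why pooling or fitted accuracy is needed.

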Design. A group of 6 hemianopic participants will be pre-screened for suitability and baseline (pre-training) performance will be acquired on the battery of visual tasks (see below) and be administered the low-vision visual functioning questionnaire (LV-VFQ-48) to assess quality of life, a dilated ophthalmic exam including Optical Coherence Tomography of the macula/RNFL, a kinetic visual field test with size V, and a 30-2 humphrey visual field with Size V. If the participant has a recent 30-2 exam on file, this may be used instead of collecting a new exam. Participants will receive a second kinetic visual field test and a 30-2 visual field test at the end of the study to measure any changes according to the clinical standard.

They will participate in weekly sessions (1.5-2 hrs) for the next three months. This purposely extends well beyond the window of expected recovery. In initial (“training”) sessions, subjects will be exposed (and respond) to spatiotemporally congruent pairs of visual-auditory stimuli presented within their blinded field, with occasional probes of unisensory visual stimuli on both sides of space. Once recovery of visual responsiveness in the contralesional field is observed, sessions will alternate between “training/testing” and “testing only” sessions in which performance on the visual battery will be re-assessed. Because this is a pilot study, the testing battery is extensive. However, the principal hypotheses and predictions are qualitative: subjects will either be able to perform a visual task at some level or not at all.

A high-speed digital video camera mounted behind the participant will record overt movements for later analysis using manual or automated scoring. The subject’s face is not included on the video, however, the video obtained contains potentially identifying information and will be secured on an encrypted drive. Multiple data points will be extracted: latency of the initiation of the motor movement, during of execution, and final position. These multiple measures will then be analyzed alongside other data points for the subject after anonymization to determine their changes during the course of experimentation and prognostic value in treatment outcomes.

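### Maximum likelihood with six subjects understates between-subject variances by about one sixth, and the plan names no small-sample correction or random-effects structure

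*Combined protocol and SAP*

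**What the plan says.** The sample size is given in the Design paragraph of Methods and Measures: "A group of 6 hemianopic participants will be pre-screened for suitability". Subjects selection criteria and Subject Recruitment Methods both put it this way: "Multiple (n=6) subjects will be recruited for left- and right-sided lesions".

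The Analytical Plan describes the quantitative model: "Parameters of these functions describing thresholds and maximum accuracy will, alongside confidence scores and latency, be evaluated for changes over time", and this is done "across subjects and sides of space in a multilevel multivariate regression model". The estimation method and its purpose follow: "Maximum likelihood estimation will be used to estimate parameter distributions to guide future studies".

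The plan does not say which effects vary by subject, what covariance structure they have, how intervals are formed, or what happens if a fit is singular or does not converge. It mentions neither REML, nor a prior, nor small-sample degrees of freedom. The only limit on estimation that it admits concerns demographic factors, which "will be noted but are unlikely to be able to be statistically evaluated".

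**The concern.** Maximum likelihood estimates variances as if the fixed effects were known. In a large study the loss is trivial. With six subjects, one estimated mean uses one of six subject-level degrees of freedom, so the variance between subjects is too small on average. Standard errors and default intervals for effects that vary between people are then too small as well.

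This matters because supplying estimates to later studies is the stated purpose of the fit. The between-subject spread of the training effect is one of the most useful things a pilot can pass on, and it is the quantity that six subjects determine least well. A joint model of four outcomes may also ask for more between-subject covariance than six people can provide, and the plan sets no limit on this.

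**Working it through.** The documents give no standard deviation, interval, significance level or sample-size calculation for this model, so there is no figure to reproduce.

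**Inputs**
- Subjects: n = 6 (Design). n = 12 is a less natural reading of the recruitment wording and is shown for sensitivity.
- Outcomes: at least 4, namely threshold, maximum accuracy, confidence and latency (Analytical Plan).
- Occasions per subject: "They will participate in weekly sessions (1.5-2 hrs) for the next three months" gives about 12 sessions. Testing alternates with training, so T = 6 to 12 usable occasions is assumed.
- Assumed, not in the documents: intraclass correlation (ICC) 0.2, 0.5 or 0.8; correlation 0.3 between random effects.

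**1. Variance bias.** In a balanced design with subject-level variance σb², residual variance σe² and one subject-level mean, the interior maximum likelihood estimate has expectation

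(n − 1)/n × σb² − σe²/(nT).

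- The leading factor at n = 6 is 5/6 = 0.833, or 17% low. On the SD scale it is √0.833 = 0.913, or about 9% low.
- The second term is small. With ICC 0.5 and T = 12 it is 1/72 = 0.014 of σb², giving 0.833 − 0.014 = 0.819.
- At n = 12 the leading factor is 11/12 = 0.917.
- As a check, 300 mixed-model fits were simulated (6 subjects, 12 occasions, random intercept and slope, true variances 1.0). Mean variances under maximum likelihood were 0.85 (intercept) and 0.80 (slope); under REML they were 1.03 and 1.00. Many of these fits gave convergence warnings, so they only support the formula.
- The bias is an average. The estimate falls below the truth in about 69% of samples.

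**2. Coverage, if Wald z intervals are used.** Coverage of a nominal 95% interval for a between-subject mean is P(|t5| < 1.96 × √(5/6)) = P(|t5| < 1.789) = 0.866. The simulated fits gave 87.0%.
- REML with z: P(|t5| < 1.96) = 0.893, so REML alone is not enough.
- REML with t on 5 degrees of freedom: 95% in the balanced case. The maximum likelihood z interval has 1.96 × 0.913 / 2.571 = 0.70 of that half-width.
- At n = 12, maximum likelihood with z covers 91.3%.

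**3. Singularity, by random structure.** With an intercept and time slope for four outcomes there are 8 random effects and 8 × 9/2 = 36 covariance parameters. Once means are removed, the between-subject scatter of six subjects has rank at most 6 − 1 = 5, so an unstructured 8 × 8 estimate must be singular.

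For smaller structures the answer depends on within-subject noise. Share of singular maximum likelihood fits in 2,000 simulated data sets per setting, n = 6:

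| Random effects | T | ICC 0.2 | ICC 0.5 | ICC 0.8 |
|---|---|---|---|---|
| 4 (intercepts only) | 6 | 99% | 85% | 43% |
| 4 (intercepts only) | 12 | 96% | 63% | 27% |
| 2 | 6 | 60% | 17% | 2.5% |
| 2 | 12 | 38% | 7% | 0.5% |
| 1 | 6 | 21% | 2% | 0.2% |
| 1 | 12 | 8% | 0.8% | 0.1% |

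REML changes this little: with 4 random effects, T = 12 and ICC 0.5, the share is 58% instead of 63%.

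**4. Precision of an unbiased SD.** With 5 degrees of freedom and little within-subject noise, the 95% limits are √(5/χ²(0.975)) = 0.62 and √(5/χ²(0.025)) = 2.45 times the estimate.

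**5. Illustration for a later trial.** Assume a true standardised difference of 0.5, two arms, 80% power, two-sided 0.05, and an outcome SD taken wholly from the between-subject variance.
- Needed per arm: 2 × (1.96 + 0.842)²/0.25 = 62.8, so 63.
- With the variance at 5/6: 62.8 × 5/6 = 52.3, so 53.
- True power at 53 per arm: Φ(0.5 × √(53/2) − 1.96) = Φ(0.61) = 0.73.

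**The case against.** The best defence is that little in this pilot depends on the model. The Design section says: "However, the principal hypotheses and predictions are qualitative: subjects will either be able to perform a visual task at some level or not at all". Outcome Measure(s) treats recovery of any function as success, and no success criterion uses a variance component. Imprecision is also the larger problem: an SD known only to within 0.62 to 2.45 times its estimate is not rescued by removing a 9% bias. Both points stand and limit the weight of the concern. They do not remove it, because the sentence on estimation has a quantitative purpose of its own.

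A reader might infer four stronger things that the documents do not support.

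- **That the planned covariance is singular.** The plan specifies neither random slopes nor an unstructured covariance. Singularity is certain only with more than five unstructured random effects per subject. Nor does it follow from counting 10 covariance parameters against 5 degrees of freedom for four intercepts: a 4 × 4 scatter matrix on 5 degrees of freedom has full rank, and boundary fits there come from within-subject noise.
- **That the planned intervals under-cover.** No interval method is stated. The 87% applies to default Wald z intervals; t-based, profile or bootstrap intervals are not excluded.
- **That the variance is 33% low and coverage 82%.** Those figures (4/6, and t with 4 degrees of freedom) need lesion side as a subject-level covariate. Side of space, which the plan does include, varies within subject; lesion side appears only under recruitment.
- **That later trials will be under-sized.** The plan does not say that sample sizes will be computed from these variances. The 53-against-63 illustration shows only what would follow if they were.

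**Conclusion.** The concern holds in limited form. Followed as written, maximum likelihood with six subjects gives subject-level variances averaging about 5/6 of the truth, and estimates meant for later use would carry that bias with no stated correction. The 5/6 assumes a balanced design, one subject-level mean per outcome and small residual noise; residual variances, which rest on many trials, are little affected. Coverage of about 87% is conditional on Wald z intervals. Singularity is conditional on the random structure: certain for the unstructured eight-effect model, possible for smaller ones. If the plan means 12 subjects, the bias falls to about 8% and Wald coverage rises to about 91%.

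This should be corrected because a better method than the named one is available at little cost. It does not threaten the pilot's qualitative conclusions.

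**What to change.** In the Analytical Plan:

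1. Replace maximum likelihood with REML, and form intervals with Kenward-Roger or t(5)-type degrees of freedom. Both parts are needed, since REML with z still covers only 89%.
2. State the random effects and keep them within what six subjects can support, for example a subject intercept plus a subject training effect for each outcome. Add a rule for boundary or non-converged fits, because even two random effects can reach the boundary when within-subject noise is high.
3. If the joint model is wanted, fit it with stated weakly informative priors. There is a reason to want it: The Expected Result predicts that performance will recover before confidence, which is a cross-outcome question.
4. Report each between-subject SD with its interval, alongside all six subject-level estimates, so that a later study can plan from the range and not only from the point estimate.

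The change takes a few sentences and no new data. The price is wider intervals and, if outcomes are modelled separately, no estimated cross-outcome covariance. With priors, the variance estimates will depend partly on the priors chosen, so these need to be reported.
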